10.4.8.1 Radiological assessment of tumours during long term follow up period (Visit 11-16)

Radiological assessments will be at the discretion of the investigator. The disease status assessment will be based on local radiology results. No central radiographic assessment will be undertaken during the long term follow up period.

10.4.9 Radiation Oncology Expert Committee

A Radiation Oncology Expert Committee (ROEC), comprising medical Oncologists, Radiation Oncologists and Radiologists independent of the study sponsor, will be formed to assess clinical progression of patients on the study. The ROEC will receive copies of all CT/MRI scans (including any with RECIST measures), PSA measures, ECOG and pain score measurements for review and provide an assessment of overall clinical evaluation of response per patient which will be documented according to sponsor guidelines. This assessment will be used to support the definition of endpoints for future studies.

11 DATA COLLECTION AND MANAGEMENT

11.1 METHODS

It is the responsibility of the Principal Investigator to ensure that there will be primary source documentation for all patient data collected as part of the study, and the data will not be recorded onto the eCRFs without the availability of such primary documentation. For this study, there is no data which has been permitted for direct data entry without source documentation. The source data may include such documents as clinical notes, laboratory result sheets, pathology reports, radiology results, etc., and will be retained in each patient's medical record or research chart. CRFs will be provided by the Sponsor.

The Principal Investigator or delegate/s will be responsible for the timeliness, completeness, and accuracy of the information entered on the CRF. The Principal Investigator will provide

access to the Medical Monitor or designated Sponsor representative(s) for the periodic review of all study records, source documents among other records for review and inspection to assure accuracy and completeness of the CRFs. All CRFs will be 100% source verified against corresponding source documentation (e.g., office and clinical laboratory records) for each patient.

The Sponsor and designated Sponsor representative(s) will maintain frequent contact with each site to assure the study is conducted according to the protocol and that all data collected are accurate and complete. Any deficiencies identified during the study will be communicated to the site for prompt correction.

11.1.1 Case report form

All information relative to the study will be recorded into a 21 CFR part 11 FDA compliant electronic Case Report Form (CRF). Data corrections will be entered by the authorised site personnel.

11.1.2 Return and storage of forms

The Investigator will retain the copies of the CRF and all other study related documents for 15 years from completion of the study.

11.2 DATA MANAGEMENT

11.2.1 Data Coding

Medications will be coded from the WHO Drug Dictionary and medical history and adverse events will be coded using the MedDRA terminology for System Organ Class (SOC) and Preferred Term (PT).

11.2.2 Data validation

A Data Management Plan which fulfils the requirements for ICH GCP will be developed to describe all manual and electronic validation checks of the data prior to analysis. Data queries requiring clarification will be documented on the EDC eCRF for the investigational site to resolve. Only authorised personnel will make corrections to the clinical database, and all corrections will be documented in an electronic audit trail.

12 STATISTICAL SECTION

12.1 SAMPLE SIZE

The study is intended as a Proof of Concept and dose confirmation study, providing justification for and guidance on the design of further studies.

The primary objective of this study is to observe safety and tolerability of idronoxil (NOX66) in combination with radiation therapy (at palliative doses). In conjunction with observations

from the other phase 1 trials in the NOX66 development program, 24 patients are considered adequate to inform on toxicity and safety in order to progress to phase 2/3.

Palliative Radiation therapy alone is unlikely to provide more than a minor and temporary reduction (<30%) in tumour size. Any responses greater than this will be considered to be related to NOX66 use. Any signals of efficacy will be described in the Clinical Study Report and used to support the Phase 2/3 development program.

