5 STUDY RATIONALE

5.1 RATIONALE FOR COMBINATION WITH RADIATION THERAPY

5.1.1 Radio-sensitisation

Many cancer patients receive radiation therapy, either as part of a treatment regimen or in the palliative setting, to reduce tumour size and manage pain and symptoms associated with end stage cancer.²⁸

The anti-cancer effect of ionizing radiation relates to its ability to cause double strand breaks in DNA, and the non-specificity of this effect means that the dosage of radiation able to be applied is self-limiting. This dosage limitation is exacerbated by the presence of factors (radio-resistance) that render some cancer cells less sensitive to the damaging effects of ionizing radiation, while normal cells are without those same factors and retain full radio-sensitivity, as discussed in Section 5.1.

The use of NOX66 as a tumour cell-specific sensitiser of radiation therapy may provide greater response to targeted radiation therapy within the tumour cells, with the tumour specific nature of NOX66 activity leading to no greater effect on non-tumour cells. As such, NOX66 is expected to increase the response to palliative dose radiation therapy, reducing target tumour size beyond those expected with palliative radiation therapy alone, with no significant increase in serious and severe adverse events.

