6.2 SECONDARY OBJECTIVES

- To investigate whether idronoxil administered as the NOX66 formulation will sensitise end stage prostate cancer to palliative radiation therapy and provide a clinically relevant response to treatment according to:
 - RECISTv1.1 criteria for measurable lesions, within irradiated and non-irradiated target lesions
 - Improvement in total pain scores using BPI-SF instrument
 - To observe changes in serum PSA
 - Review of CT/MRI scans by Radiation Oncology Expert Committee –assessment of observable and or symptomatic changes from baseline over time
- To determine a dose of NOX66 to continue into late phase clinical trials
- To investigate plasma idronoxil levels following NOX66 therapy
- To determine Progression Free Survival (PFS) and Overall Survival (OS)

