7 STUDY DESIGN

This is an open-label Phase Ib dose confirmation and proof of concept study in up to 24 patients with end stage castrate resistant prostate cancer who are being considered for or undergoing palliative radiation therapy for pain and symptom management. Patients will have a minimum of one (1) lesion which is amenable to radiation therapy. Palliative RT (20Gy over 5 fractions) will be delivered to selected lesion in combination with rectally administered idronoxil (NOX66).

This study is intended to provide information regarding the safety of this treatment combination and justification for a larger Phase 2/3 study in the treatment of patients with combination of NOX66 and palliative radiation therapy.

Clinical response to treatment will be assessed by radiological CT/MRI scans, where applicable objectively measures by RECISTv1.1, by pain response as evaluated by Brief Pain Inventory Short Form, ECOG scores and by monitoring PSA as surrogate marker with overall (observable and symptomatic) response based on data review by an independent Radiation Oncology Expert Committee (ROEC). Local response will be based on investigator review of data in conjunction with ROEC.

PSA will be monitored as a surrogate marker of response and pain response will be evaluated using the Brief Pain Inventory Short Form throughout the study.

Patients will be suitable for the study as they become eligible for, and will be given, palliative radiation therapy for management of their cancer.

Three dose cohorts will be investigated in this study with dosing based on criteria outlined in section 10.2.7. The three doses of idronoxil investigated include:

- 400mg idronoxil provided as one NOX66 suppository per day
- 800mg idronoxil provided as one NOX66 suppository twice daily
- 1200mg idronoxil provided as one NOX66 suppository three times daily.

Treatment will be for one cycle of combined radiation therapy and NOX66 with follow up assessments at Week 6, Week 12, Week 24 and every 3 months for the following 18 months. All patients will be followed up for disease progression and survival information either by retrospective review of medical records or by a physical visit or by telephone follow up call.

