10.2.14 Cohort Allocation and Dose Escalation

[figure not shown]
This study will enrol up to 24 patients across three dose levels of NOX66. Dose cohort assignment will be sequential and dose escalation decisions will be based on patients who experience adverse events directly related to NOX66 treatment and discontinued as described below and outlined in Figure 2.

Dose escalation and decision rules are as follows:

- **Patients 1-4 (Dose Cohort 1)** will be prescribed NOX66 400mg.
- **Patients 5-8 (Dose Cohort 2):** Once fourth patient in Cohort 1 has completed treatment (Visit 7), the dose of NOX66 for next cohort, patients 5-8, will be as determined as follows, based on the number of discontinuations due to NOX66 related adverse events:
 - If no patients discontinue treatment, NOX66 dose will be increased to 800mg
 - If one patient discontinues treatment, NOX66 dose will remain at 400mg
 - If more than one patient discontinues treatment, there will be no further recruitment to the study until scans from WEEK 6 are assessed for disease status
- **Patients 9-12 (Dose Cohort 3):** Once the eighth patient in Cohort 2 has completed treatment (Visit 7), the dose of NOX66 for next cohort, patients 9-12, will be as determined as follows, based on the number of discontinuations due to NOX66 related adverse events:
 - If no patients in Dose Cohort 2 discontinue treatment, NOX66 dose will be increased (from 400mg to 800mg or from 800mg to 1200mg)
 - If one patient in Dose Cohort 2 discontinues treatment, NOX66 dose will remain at the same dose (400mg or 800mg)
 - If more than one patient in Dose Cohort 2 discontinues treatment, dose will be reduced (from 800mg to 400mg) or, if dose has remained at 400mg, there will be no further recruitment to the study until scans at WEEK 6 are assessed for disease status.

Following the review of all accumulated safety data, disease status and treatment efficacy signals from scans assessed per RECIST 1.1 criteria and preliminary pain response at WEEK 6 for all patients, the Study Steering Committee will determine the dose at which to continue treatment for the expansion patient Cohort 4 in the study. A further 12 patients will be recruited at this dose level.

Figure 2: Dose Escalation and Dose Expansion Schema

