12.2 STATISTICAL METHODOLOGY

This section describes the planned statistical analyses in general terms. A complete description of the statistical analysis will be specified in a statistical Analysis Plan (SAP) finalised prior to completion of the study.

General: Data will be summarized by using counts and percents for discrete parameters, and by descriptive statistics (e.g. number of observations, mean, standard deviation, median, minimum and maximum) for continuous parameters. Subject disposition and baseline characteristics will be presented for all treated patients. Data will be analysed as collected. No imputation of values for missing data will be performed. Standard clinical monitoring and data management practices will be used to ensure the integrity of the data.

Populations for analysis: There will be two study populations defined for this study. The safety population will consist of all patients who received at least one dose of NOX66. This population will be used in all safety summaries. The efficacy population will consist of all patients who complete radiation therapy with at least 7 days of NOX66 dosing.

Baseline Comparisons and Patient Disposition: Demographic and baseline disease characteristic data summarisation will be performed in order to descriptively document any safety and efficacy findings. Data to be tabulated will include demographic features such as age and race, as well as medical history. The number and percentage of patients who complete the study or who withdraw for any reason will be presented.

Efficacy Analysis: Results from (i) RECIST 1.1 response assessment for target lesions and non-target lesions, (ii) ECOG Performance Score and (iii) Pain scores. Changes from baseline in levels of serum PSA levels will be listed.

Overall and progression-free survival, PSA and pain scores collected during the extended follow-up period will be summarized in the same manner as for the immediate post-treatment follow-up period.

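### Section 12.1 credits any tumour shrinkage of 30% or more to NOX66, although every patient also receives radiotherapy and no radiotherapy-alone response rate is given

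*Combined protocol and SAP*

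**What the plan says.** Section 12.1 makes two consecutive statements about tumour size. The first is hedged: "Palliative Radiation therapy alone is unlikely to provide more than a minor and temporary reduction (<30%) in tumour size". The second is not: "Any responses greater than this will be considered to be related to NOX66 use". The section then says that efficacy signals will be described in the Clinical Study Report and used in support of Phase 2/3 development.

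The treatment plan gives everyone both components. Section 7 describes one cycle of RT (20 Gy in 5 fractions) combined with NOX66 at 400, 800 or 1200 mg daily. Section 10.2.14 states: "This study will enrol up to 24 patients across three dose levels of NOX66". Section 8.1 rules out randomisation. In section 12.2, "The efficacy population will consist of all patients who complete radiation therapy with at least 7 days of NOX66 dosing".

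Section 5.1.1 says that RT is itself used "in the palliative setting, to reduce tumour size and manage pain and symptoms associated with end stage cancer", and it expects NOX66 to act by "reducing target tumour size beyond those expected with palliative radiation therapy alone". The related secondary objective in section 6.2 is "To investigate whether idronoxil administered as the NOX66 formulation will sensitise end stage prostate cancer to palliative radiation therapy".

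**The concern.** The first sentence of the pair allows that RT alone will sometimes produce 30% shrinkage. The second allows no such case. A response in an irradiated lesion has two candidate causes, and the rule assigns it to one of them by definition. For the tumour-size part of the sensitisation objective, that assumes the answer to the question under study.

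What is at stake is the interpretation carried into the study report and then into the case for Phase 2/3. Followed as written, a response that RT alone would have produced is reported as evidence for the drug.

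**Working it through.** **1. What the threshold catches.** Section 10.4.8 defines partial response as a decrease of at least 30% in the sum of longest diameters. The ceiling in 12.1 is a reduction below 30%. The two cut-offs coincide, so the rule covers essentially every partial or complete response in irradiated target lesions.

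**2. Is there an internal comparison?** Planned patients: 3 × 4 + 12 = 24, which agrees with the stated total. All receive NOX66 at a non-zero dose together with RT. No group receives RT alone, and the efficacy population requires both treatments.

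**3. Is there an external benchmark?** Neither 5.1.1 nor 12.1 gives an RT-alone response rate or a source for the 30% ceiling. The only outside response rate in the rationale is 11/41 = 27% in section 5.1.2. That is an abscopal rate under chemotherapy, RT and GM-CSF, so it is no benchmark for RT alone.

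**4. Illustration of size.** Two inputs are assumptions, because the documents do not give them:
- p0, the proportion of patients in whom RT alone gives at least 30% shrinkage, taken as 2%, 5% and 10%.
- n, the number of patients with measurable irradiated lesions, taken as 6, 12 and 24. Measurable disease is not an entry criterion in section 8.2, so 24 is the upper limit.

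If NOX66 adds nothing, the expected number of false attributions is n × p0. At p0 = 5% this is 6 × 0.05 = 0.3, 12 × 0.05 = 0.6 and 24 × 0.05 = 1.2.

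The chance of at least one is 1 − (1 − p0)^n. For example, with n = 24 and p0 = 5%, it is 1 − 0.95^24 = 0.708. The chance of at least two also subtracts n × p0 × (1 − p0)^(n−1).

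| n | At least one, p0 = 2% / 5% / 10% | At least two, p0 = 2% / 5% / 10% |
|---|---|---|
| 6 | 0.114 / 0.265 / 0.469 | 0.006 / 0.033 / 0.114 |
| 12 | 0.215 / 0.460 / 0.718 | 0.023 / 0.118 / 0.341 |
| 24 | 0.384 / 0.708 / 0.920 | 0.083 / 0.339 / 0.708 |

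**5. How much evidence one response carries.** The rule credits NOX66 from the first response. The exact (Clopper-Pearson) 95% intervals for a single responder are 1/6: 0.4% to 64%; 1/12: 0.2% to 38%; 1/24: 0.1% to 21%. The lower limit first exceeds an assumed p0 of 5% at 3/6 (11.8%), 3/12 (5.5%) or 5/24 (7.1%). For p0 of 10% the counts are 3/6 (11.8%), 5/12 (15.2%) or 7/24 (12.6%). This is for scale only, since the plan proposes no test.

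**6. Non-irradiated lesions.** Section 5.1.2 describes abscopal responses to RT as rare, so the RT-alone explanation is weaker there. The point bears chiefly on irradiated lesions.

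**The case against.** The strongest reply is that the sentence does nothing operational. No analysis in 12.2 uses it, and neither do the dose decisions in 10.2.14 and 13.2. The sample size rests on a judgement about safety. Efficacy is secondary and the synopsis plans description only, so the tabulated RECIST categories would be the same without the sentence. All of this is true, and it limits the severity. It does not rescue the sentence, which is a pre-stated interpretation in the statistical section, placed directly before the reference to Phase 2/3.

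Other text is more cautious. Section 4 says NOX66 may sensitise tumours, and section 5.4 says the efficacy of the combination is unknown. These passages soften the tone without withdrawing the rule.

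Section 4 also plans to look for efficacy differences across the three doses, which is some internal contrast. With four patients per non-randomised escalation cohort it is too weak to validate the attribution.

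The illustrative probabilities rest on assumed inputs and span 11% to 92%. That is a fair criticism of the numbers. The argument does not need them, because with no RT-alone rate stated, the attribution is unsupported at any value.

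The rule also makes no exception for a response first seen after another anti-cancer therapy. This gap is narrowed by the exclusion of concurrent systemic chemotherapy or biological therapy (8.3) and the limits in 9.6, but it is not closed. It is a secondary matter.

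**Conclusion.** The concern holds. The attribution sentence is wrong as written: a design in which every patient gets both treatments, with no RT-alone rate from inside or outside the study, cannot assign responses in irradiated lesions to NOX66.

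The consequence is limited to interpreting tumour response and to its later use in support of Phase 2/3. The primary safety objective, the escalation rules, and the pain and PSA results are unaffected. The probabilities above show sensitivity to assumed values of p0 and n; they do not show that a false attribution is likely in this trial. The sentence should be corrected, but it does not threaten the study.

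**What to change.** Delete the attribution sentence in 12.1 and replace it with, for example: *Responses are attributed to the combination of NOX66 and RT; this uncontrolled study cannot isolate the contribution of NOX66.* In the SAP that 12.2 says will be finalised later, report response counts among patients with measurable target lesions, separately for irradiated and non-irradiated lesions. Sections 6.2 and 10.1 already make that split, so no new data are needed.

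Two additions are optional. Exact 95% intervals would show how little a few responses establish. Responses first seen after a new anti-cancer therapy could be flagged, from the concomitant-medication records (9.6, 12.2) up to Week 24 and from the long-term follow-up records (10.2.7 to 10.2.13) afterwards. The records in 9.6 name only medications, so further radiotherapy or surgery before Week 24 might be missed. No formal test is needed.

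The cost is one sentence in the protocol, a short SAP entry and a weaker efficacy statement. If intervals are shown, they will be wide.

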12.2 STATISTICAL METHODOLOGY

This section describes the planned statistical analyses in general terms. A complete description of the statistical analysis will be specified in a statistical Analysis Plan (SAP) finalised prior to completion of the study.

General: Data will be summarized by using counts and percents for discrete parameters, and by descriptive statistics (e.g. number of observations, mean, standard deviation, median, minimum and maximum) for continuous parameters. Subject disposition and baseline characteristics will be presented for all treated patients. Data will be analysed as collected. No imputation of values for missing data will be performed. Standard clinical monitoring and data management practices will be used to ensure the integrity of the data.

Populations for analysis: There will be two study populations defined for this study. The safety population will consist of all patients who received at least one dose of NOX66. This population will be used in all safety summaries. The efficacy population will consist of all patients who complete radiation therapy with at least 7 days of NOX66 dosing.

Baseline Comparisons and Patient Disposition: Demographic and baseline disease characteristic data summarisation will be performed in order to descriptively document any safety and efficacy findings. Data to be tabulated will include demographic features such as age and race, as well as medical history. The number and percentage of patients who complete the study or who withdraw for any reason will be presented.

Efficacy Analysis: Results from (i) RECIST 1.1 response assessment for target lesions and non-target lesions, (ii) ECOG Performance Score and (iii) Pain scores. Changes from baseline in levels of serum PSA levels will be listed.

Overall and progression-free survival, PSA and pain scores collected during the extended follow-up period will be summarized in the same manner as for the immediate post-treatment follow-up period.

Safety Analysis: The safety will be assessed through the analysis of the reported incidence of treatment emergent AEs, including SAEs, dose-limiting toxicities, AEs leading to withdrawal, events of at least CTCAE Version 4.03 Grade 3 in severity, and AEs related to study treatment. Treatment emergent AEs are those with an onset on or after the initiation of therapy. Other safety endpoints include laboratory results, physical examinations, vital signs, and changes in ECOG status. A copy of CTCAE Version 4.03 scoring system may be downloaded from:

http://evs.nci.nih.gov/ftp1/CTCAE/CTCAE_4.03_2010-06-14_QuickReference_8.5x11.pdf.

The adverse events will be summarized by MedDRA coding terms, System Organ Class (SOC), and preferred term for all treated patients and by dose cohort. The AEs will also be tabulated by maximum severity and maximum relationship to study drug where applicable. The number and percent of patients experiencing dose-limiting toxicities will be summarized by dose cohort, by DLT, and system organ class for all treated patients. Other safety endpoints, which include change from baseline in laboratory results and vital signs, and shifts in physical examinations, will be summarized throughout the study by visit for each dose level for all treated patients.

Concomitant medications: are to be listed for all patients.

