8.4 SCREEN FAILURE AND STUDY WITHDRAWAL

Patients should begin protocol treatment within 2 weeks of enrolment at screening. Issues that would cause treatment delays longer than 2 weeks should be discussed with the Sponsor. If a patient does not proceed to receive protocol therapy following enrolment at screening, the patient's study enrolment will be cancelled, and the patient will be considered a screen failure. The Sponsor should be notified of screen failures as soon as possible.

Patients will be informed that they are free to withdraw from the study at any time and for any reason. Withdrawal criteria, other than progressive disease, can be defined as one or more of the following:

- an inter-concurrent illness that prevents further administration of idronoxil (NOX66) or radiation therapy;
- an adverse event to the combination treatment that is intolerable;
- the patient withdraws consent;
- the patient dies;
- general or specific changes in the patient's condition render the patient unacceptable for further treatment in the judgment of the Investigator.

In all cases, the reason for withdrawal must be recorded in the CRF and in the patient's medical records. The patient must be followed to establish whether the reason was an adverse event causally related to idronoxil (NOX66), and, if so, this must be reported in accordance with the requirements for adverse event reporting.

Patients will continue to be followed for the duration of the study, unless consent is withdrawn.

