8.5 PATIENT REPLACEMENT

Patients who cannot be evaluated as part of the efficacy analysis may be replaced in the study at the discretion of the Sponsor.

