9.4 TREATMENT DOSE MODIFICATIONS AND TREATMENT CYCLE DELAY

9.4.1 NOX66

Any patient who experiences toxicity > Grade 2 related to NOX66 will have the idronoxil treatment withheld for 1 day and then resume on the next lower dosage (1200 mg reduced to 800 mg; 800 mg reduced to 400 mg; 400 mg daily reduced to 400 mg every 2nd day) for the remainder of the treatment period.

If toxicity > Grade 2 persists following reduction of dose, the idronoxil treatment will cease immediately for the remainder of the treatment period, although the patient may remain in the study.

There will be no dose modification of NOX66 on the basis of body weight.

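### The efficacy population in 12.2 is defined by treatment completion, so treated patients who stop early leave the efficacy denominator even when followed and scanned

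*Combined protocol and SAP*

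**What the plan says.** Section 12.2 defines two populations. The safety population is everyone with at least one dose of NOX66, and it is assigned to the safety summaries. The other is given as: "The efficacy population will consist of all patients who complete radiation therapy with at least 7 days of NOX66 dosing". No third population and no all-treated efficacy summary is named. The same section sets the form of reporting: "Data will be summarized by using counts and percents for discrete parameters". Sections 12.2 and 12.3 both rule out imputing missing values.

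Other sections bear on who is left out:

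- Section 8.4, on patients who withdraw: "Patients will continue to be followed for the duration of the study, unless consent is withdrawn".
- Section 9.4.1, when toxicity above Grade 2 persists after dose reduction: "the idronoxil treatment will cease immediately for the remainder of the treatment period, although the patient may remain in the study".
- Section 9.4.1, on the reduction step for the lowest dose: "400 mg daily reduced to 400 mg every 2nd day".
- Section 9.3 schedules scans at Weeks 6, 12 and 24 and does not make them depend on completing treatment.
- Section 8.5: "Patients who cannot be evaluated as part of the efficacy analysis may be replaced in the study at the discretion of the Sponsor".

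Section 12.1 takes radiotherapy alone as unlikely to shrink tumours by 30% or more. It then says: "Any responses greater than this will be considered to be related to NOX66 use". It adds: "Any signals of efficacy will be described in the Clinical Study Report and used to support the Phase 2/3 development program".

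**The concern.** Both entry conditions are post-baseline events. A patient who meets them stays in, even if NOX66 stops later. A patient who stops before meeting either one is removed, and the reasons for stopping listed in 8.4 (intercurrent illness, intolerable adverse events, deterioration, death) can be related to outcome. The plan may therefore collect outcome data that its only efficacy population discards.

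The direction of the bias cannot be fixed in advance. Rates read high if those left out respond less often, for example after stopping for deterioration or death. They could read low if those patients do respond: section 5.3 expects adverse events beyond the usual level to go with greater efficacy.

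Two features add to this. Section 8.5 does not say whether a replaced patient stays in the efficacy summaries. And if the 7 days are days on which a dose is taken, which the plan does not say, the reduction schedule in 9.4.1 makes the threshold harder to reach at 400 mg than at the higher doses.

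With no control arm, the observed responses carry the whole efficacy argument for Phase 2/3.

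**Working it through.** **Plan's own figure.** 3 cohorts × 4 + 12 = 24, which matches the stated total. The plan gives no expected size for the efficacy population, early-stopping rate or target response rate, so there is nothing further to reproduce. All counts of responders, exclusions and target lesions below are assumptions.

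**When membership is settled.** Sections 9.3 and 10.2.3 give five fractions over five to eight days from Day 2, so the last fraction falls between Day 2 + 5 − 1 = Day 6 and Day 2 + 8 − 1 = Day 9. Without interruption the 7th NOX66 day is Day 7. Most patients therefore qualify between Day 7 and Day 9. Section 10.1 counts survival and progression-free time from treatment start, before that point.

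**How many might be excluded.** With an assumed early-stopping rate p, the expected number among 24 is 24p and the chance of at least one is 1 − (1 − p)^24:

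| p | Expected exclusions | Chance of at least one |
|---|---|---|
| 5% | 1.2 | 71% |
| 10% | 2.4 | 92% |
| 15% | 3.6 | 98% |

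**Effect on a response rate.** Suppose 6 of 24 treated patients respond: 6/24 = 25.0%, exact (Clopper-Pearson) 95% interval 9.8% to 46.7%. With k patients excluded, of whom r respond, the reported rate is (6 − r)/(24 − k).

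| Excluded (k) | Responders among them (r) | Reported |
|---|---|---|
| 1 | 0 | 6/23 = 26.1% |
| 2 | 0 | 6/22 = 27.3% |
| 4 | 0 | 6/20 = 30.0% |
| 2 | 1 | 5/22 = 22.7% |
| 2 | 2 | 4/22 = 18.2% |

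In a single cohort of 4 with 1 responder, losing one non-responder moves 1/4 = 25.0% to 1/3 = 33.3%.

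**Replacement.** Suppose 1, 2 or 4 patients are replaced, none of them responds, and 6 of the 24 kept respond. The report shows 6/24 = 25.0%. Among all treated patients the rate is 6/25 = 24.0%, 6/26 = 23.1% or 6/28 = 21.4%.

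**RECIST rates.** These use only patients with target lesions, a number the plan does not give. Dropping one non-responder moves 2/8 = 25% to 2/7 = 28.6%, 3/12 = 25% to 3/11 = 27.3%, or 4/16 = 25% to 4/15 = 26.7%.

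**Dose-dependent exclusion, if the 7 days are dosing days.** Let toxicity follow the dose on Day k (k = 1 to 6), with Day k + 1 withheld and dosing resumed on Day k + 2; 7 − k further dosing days are needed.

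- Starting at 800 or 1200 mg (daily after reduction): the 7th dosing day is (k + 2) + (7 − k) − 1 = Day 8.
- Starting at 400 mg (every 2nd day after reduction): it is (k + 2) + 2(7 − k − 1) = Day 14 − k, from Day 13 (k = 1) to Day 8 (k = 6).

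Take k = 1 with NOX66 stopped after Day 9. The higher doses give Day 1 and Days 3 to 9, which is 8 dosing days, so the patient is kept. At 400 mg the days are 1, 3, 5, 7 and 9, which is 5, so the patient is left out.

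**The case against.** The strongest reply is that the harm is limited and partly inferred. Section 12.2 assigns the safety population to the safety summaries but has no matching sentence for the efficacy population, and it leaves full detail to a later SAP. The synopsis reports each patient's response and lists outcomes per patient. The expert committee assesses all patients (synopsis and 10.1), and the expansion-dose review at Week 6 uses all patients (10.2.14 and 13.2). Disposition is shown for all treated patients, and ECOG change is also a safety endpoint. Efficacy is secondary and descriptive, with no test and no go/no-go threshold. The attribution rule in 12.1 concerns individual responses rather than a rate. An exposure-defined set is also a coherent choice for asking whether the combination, once delivered, shows a signal.

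Much of this stands. A reader could rebuild a denominator from the listings, and the expansion decision does not appear to depend on this definition. The dose-level example needs a particular reading of the 7 days and a particular course of events. Section 8.5 does not say that being unevaluable means failing the 12.2 definition, and the replacement figures go beyond the planned maximum of 24.

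It does not remove the point. None of these features sets the denominator for the counts and percentages in 12.2. No other efficacy population is offered, so a SAP that follows 12.2 inherits the exclusion. An exposure-defined set can still be shown, but as support for an all-treated result.

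**Conclusion.** The concern holds. The only population named for efficacy selects on post-baseline treatment completion and leaves out treated patients whose outcomes the plan may well have. It should be changed, but it does not threaten the primary safety objective, which uses every dosed patient.

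The size is unknown and probably modest. Excluding up to 4 non-responders moves an assumed 25.0% by 1.1 to 5.0 percentage points, and excluding responders moves it the other way. Every rate illustrated above lies inside the exact interval for 6/24, so the issue is avoidable selection rather than a shift that would stand out from chance in a study this small. The difference between dose levels rests on reading the 7 days as dosing days.

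**What to change.** - **12.2:** make all patients with at least one dose of NOX66 the main efficacy population (for RECIST, all such patients with a baseline target lesion). Use outcome data wherever collected, and count patients with no post-baseline assessment as non-responders. Keep the present population as supportive, state which outputs use which population, and say whether the 7 days are dosing days.
- **12.2 and 12.3:** amend the no-imputation sentences so that this responder classification is allowed. The SAP should also say how a patient with only some assessments is classified, for example one lacking the Week 12 pain score or its confirmation.
- **8.5:** state that replaced patients who received NOX66 stay in the efficacy summaries, and list exclusions and replacements by reason and dose cohort. Reconcile replacement with the stated maximum of 24 patients.

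The cost is wording in three sections, carried into the SAP still to be written, and a little more analysis. No visits or tests are added. Reported response rates will be slightly lower if the patients brought back in did not respond.
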